## VERSION TRACKING

VERSION	DATE	STATE	REASON FOR CHANGE	DESCRIPTION OF CHANGE
1.0	28 August 2017	Obsolete	N/A – new protocol	N/A
2.0	26 September 2017	Issued	To correct a typographical error in section 7.2.3.3.1., to correct [REDACTED]'s first name in Appendix XI, and to remove any reference to expiration dates in the package inserts (Appendix VIII and Appendix X).	See Summary of Changes in Appendix XII.

**SYNOPSIS**

PROTOCOL TITLE	A Randomized, Evaluator-Blinded Clinical Study to Evaluate the Efficacy and Tolerability of an Investigational Light Therapy Mask on Subjects with Mild to Moderate Mottled Hyperpigmentation and Moderate to Severe Facial Wrinkles
PROTOCOL IDENTIFICATION	CO-1705 1113 2943-SACT
SPONSOR	Johnson & Johnson Consumer Inc. 
STUDY SITE	1001 KGL Skin Study Center, LLC 
PRINCIPAL INVESTIGATOR (PI)	[name].
OBJECTIVE	The objective of this study is to evaluate the efficacy and tolerability of an investigational light therapy mask in comparison to a sham mask device over a 12-week usage period and after a 12-week regression period for subjects with mild to moderate mottled hyperpigmentation and moderate to severe facial wrinkles.
STUDY DESIGN	Single-center, 2-cell, sham-controlled, randomized, evaluator-blinded clinical usage study
STUDY POPULATION	
 
• Females, 35 to 70 years old
 
• Fitzpatrick skin types I to VI (an approximately equal number of subjects will be enrolled per skin type per cell)
 
• Clinically determined mild to moderate mottled hyperpigmentation on the face (score of 1-6 on 10-point Modified Griffiths Scale) and moderate to severe global facial wrinkling (score of 4-9 on 9-point Fitzpatrick Wrinkle and Elastosis Scale).
 

SAMPLE SIZE	A sufficient number of subjects will be screened to enroll up to approximately 125 subjects in order to finish with at least 96 subjects (targeting 48 subjects per cell with 8 subjects per Fitzpatrick skin type per cell).

INVESTIGATIONAL STUDY MATERIALS	Investigational Products (IPs) and Auxiliary Products:				
	Product	Identification Number	Product Type	Included in	
				Active Cell	Sham Cell
	AM & PM Cleanser	██████████	Auxiliary Cleanser	✓	✓
	AM Moisturizer (with SPF 30)	██████████	Auxiliary Moisturizer	✓	✓
	PM Mask Treatment	██████████	IP – Active	✓	
	PM Mask Treatment	██████████	IP – Sham		✓
	Mask Activator	██████████	IP – Active	✓	
	Mask Activator	██████████	IP – Sham		✓
DOSE AND MODE OF APPLICATION	
At Screening (Visit 1), each subject will be provided with an auxiliary cleanser and an auxiliary moisturizer to use full-face for the duration of the study. Each subject will be instructed to wash her face twice daily (morning and evening) with the AM & PM Cleanser. In the morning after washing, subjects will apply the AM Moisturizer full-face (the AM Moisturizer may be used again in the evening [after completing the mask treatment, as applicable], if desired).
 
At Baseline (Visit 2), each subject will be randomly assigned to also use either the active or sham PM Mask Treatment (with respective Mask Activator) for the 12-week treatment period of the study. In the evening after washing, subjects will use the PM Mask Treatment (either active or sham) for 10 minutes.
 
A 12-week regression period will begin at Week 12 (Visit 5); during the regression period, subjects will continue using the auxiliary products as described previously, but there will be no mask usage.
				
STUDY DURATION	
The study will consist of 6 visits* over 24 weeks with visits scheduled at Screening (Visit 1, up to 10 days prior to Baseline), Baseline (Week 0; Visit 2), Week 1 (Visit 3), Week 4 (Visit 4), Week 12 (Visit 5), and Week 24 (Visit 6). Baseline to Week 12 (Visit 2 to Visit 5) will comprise a 12-week treatment period, and Week 12 to Week 24 (Visit 5 to Visit 6) will comprise a 12-week regression period.
 
*If required for scheduling, Visits 2-6 may each be separated into up to three sub-visits (e.g. Visit 2A, 2B, and 2C) such that the imaging and subject questionnaire will occur separately from the clinical and subjective evaluations of efficacy and tolerance (which may themselves be conducted by different Expert Graders at different sub-visits, as needed). See section 7.1 for details.
				
METHODOLOGY	
 
Clinical evaluations of efficacy: fine lines, periorbital wrinkles, global wrinkling, surface roughness, uneven skin tone, mottled
 
				

	
hyperpigmentation, sallowness or yellowing, lack of radiance, [REDACTED]
 
 
• [REDACTED]
 


EVALUATION SCHEDULE
 
[REDACTED]
 
[REDACTED]
	
The clinical and subjective evaluations of efficacy [REDACTED] will be conducted at Visits 2-6 (each clinical parameter will be evaluated by the PI plus two additional board-certified dermatologist Expert Graders). [REDACTED]
 
■ The evaluations will be conducted after a 15-minute acclimation period.
 
[REDACTED]
 
[REDACTED]
 
[REDACTED]
 
[REDACTED]

SAFETY AND ADVERSE EVENTS
	
All Adverse Events (AEs) (including Serious Adverse Events (SAEs)) must be collected (occurrence date; subject identification; location; outcome; end date; and assessment of seriousness; causality; and severity) regardless of causal relationship to the subject’s participation in the study. The information should be reported within the required reporting timelines. The AEs will be included in the final study report.

STATISTICAL METHODS
	
The primary efficacy variable is the change from baseline in global wrinkling at Week 12. The mean global wrinkling change from baseline to Week 12 will be presented for each cell together with a two-sided 95% confidence interval. Superiority to baseline will be concluded if the upper bound of the 95% confidence interval for the mean change is below -5.
 
The active mask will be compared with the sham mask. Treatment means and between-treatment differences will be assessed by means of an Analysis of Covariance (ANCOVA) model with treatment and skin type group as factors and the corresponding averaged baseline score as a covariate. The two-sided 95% confidence interval for the treatment difference will be presented. Analysis of the primary efficacy variable will be based on the average scores from the three Expert Graders as well as separately for the scores from each Expert Grader.
 
Secondary variables (fine lines, periorbital wrinkles, surface roughness, uneven skin tone, mottled hyperpigmentation, sallowness or yellowing, and lack of radiance at Week 1, Week 4, Week 12, and Week 24; plus global wrinkling at Week 1, Week 4, and Week 24) will be analyzed in the same way as the primary variable.

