### **8.2.1. Analysis of Primary Variable**

The primary efficacy variable is the change from baseline in global wrinkling at Week 12. Scores from the 3 Expert Graders will be averaged for the baseline readings as well as the Week 12 readings before computing the change. For each subject, the change from baseline is then computed by subtracting post-baseline mean global wrinkling from baseline mean global wrinkling. The mean change from baseline for each cell will be presented together with a two-sided 95% confidence interval. Superiority to baseline will be concluded if the upper bound of the 95% confidence interval for the mean difference is below -0.5. The active mask will be compared with the sham mask. Treatment means and between-treatment differences will be assessed by means of an ANCOVA model with treatment and skin type group as factors and the corresponding averaged baseline score as a covariate. The two-sided 95% confidence interval for the treatment difference will be presented. Analysis of the primary efficacy variable will be based on the average scores as well separately for the scores from each Expert Grader.

If global wrinkling is missing at Week 12 for more than 5% of the subjects, the missing value will be imputed by using the last observation carried forward (LOCF) method.

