6 STATISTICAL METHODOLOGY AND STATISTICAL ANALYSES

6.1 STATISTICAL HYPOTHESES

The primary efficacy variable is the change from baseline in global wrinkling at Week 12.

Specifically, the following hypothesis will be tested to assess within-treatment changes from baseline:

$$H_0: \mu_{\text{Baseline}} - \mu_{\text{Post}} \leq 0.5$$

against the one-sided alternative

$$H_1: \mu_{\text{Baseline}} - \mu_{\text{Post}} > 0.5$$

where μ_{Baseline} and μ_{Post} are baseline mean global wrinkling and post-baseline mean global wrinkling, respectively, for active mask or sham mask treatment.

The null hypothesis that two investigational product mean efficacy variable changes from baseline are equal will be tested against the alternative hypothesis that the investigational product mean efficacy variable changes from baseline are not equal.

In other words, the following hypothesis will be tested:

$$H_0: \mu_A - \mu_S = 0$$

against the two-sided alternative

$$H_1: \mu_A - \mu_S \neq 0$$

where μ_A and μ_S are the mean changes from baseline for active mask treatment and the sham mask treatment, respectively.

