6.2 STATISTICAL DECISION RULES

Superiority to baseline will be concluded if at least two of the three Expert Graders rate the active mask superior to baseline with respect to global wrinkling at Week 12 and the mean improvement score in global wrinkling for the active mask exceeds 0.5 points at Week 12, that is the lower bound of the 95% confidence interval for the mean difference is above 0.5. (Note that under 8.2.1. Analysis of Primary Variable of the protocol it incorrectly reads that superiority to baseline will be concluded if the upper bound of the 95% confidence interval for the mean difference is below -0.5.)

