6.4.2 Primary Analysis

The primary efficacy variable is the change from baseline in global wrinkling at Week 12. Scores from the 3 Expert Graders will be averaged for the baseline readings as well as the Week 12 readings before computing the change. For each subject, the change from baseline is then computed by subtracting post-baseline mean global wrinkling from baseline mean global wrinkling. The mean change from baseline for each cell will be presented together with a two-sided 95% confidence interval.

The active mask will be compared with the sham mask. Treatment means and between-treatment differences will be assessed by means of an ANCOVA model with treatment and skin type group as factors and the corresponding averaged baseline score as a covariate. The two-sided 95% confidence interval for the treatment difference will be presented. Analysis of the primary efficacy variable will be based on the average scores as well separately for the scores from each Expert Grader.

For the secondary efficacy variables, scores from the 3 Expert Graders will be averaged for the baseline as well as each post-baseline visit before computing the change. The analyses of the secondary efficacy variables will be based on average scores and will be performed as for the primary efficacy variable.

The tertiary efficacy variable is the change from baseline at Week 1, Week 4, Week 12, and Week 24 for [REDACTED]

[REDACTED]

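### The protocol synopsis sets the within-arm superiority-to-baseline threshold at -5, ten times the figure in section 8.2.1, and the SAP's correction note does not reach it

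*Protocol*

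**What the plan says.** Four places state the within-arm rule for the primary variable.

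- **Protocol synopsis, Statistical Methods:** "Superiority to baseline will be concluded if the upper bound of the 95% confidence interval for the mean change is below -5". The synopsis does not say in which direction change is calculated.
- **Protocol 8.2.1:** "Superiority to baseline will be concluded if the upper bound of the 95% confidence interval for the mean difference is below -0.5". The same section defines change as baseline minus post-baseline, so improvement is positive.
- **SAP 6.1:** "the following hypothesis will be tested to assess within-treatment changes from baseline". The null is that baseline minus post-baseline is at most 0.5, and the one-sided alternative is that it exceeds 0.5.
- **SAP 6.2:** the averaged-score criterion is that "the mean improvement score in global wrinkling for the active mask exceeds 0.5 points at Week 12", made operational as "that is the lower bound of the 95% confidence interval for the mean difference is above 0.5".

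SAP 6.4.2 repeats the direction: "For each subject, the change from baseline is then computed by subtracting post-baseline mean global wrinkling from baseline mean global wrinkling".

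SAP 6.2 also carries a correction, which opens "Note that under 8.2.1. Analysis of Primary Variable of the protocol it incorrectly reads" and goes on to cite the -0.5 wording. It does not mention the synopsis. The version tracking table and Appendix XII of the protocol list the version 2.0 changes: one item in section 7.2.3.3.1, one contact name, and the package inserts. None touches the synopsis.

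SAP 6.2 adds a condition found in neither protocol statement of the rule: "at least two of the three Expert Graders rate the active mask superior to baseline with respect to global wrinkling at Week 12".

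**The concern.** The current protocol carries two thresholds, ten times apart, for one decision on the primary variable. The sponsor noticed an error in this rule while writing the SAP and corrected one of the two places where it appears. The uncorrected place is the summary that many readers consult first. A reader who takes the success criterion from there would judge the within-arm result against a figure that the rest of the plan does not use, in a form that the SAP has rejected.

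A smaller point concerns the two-of-three-grader condition. It does not say what test or margin makes a single grader's result superior to baseline, and the SAP note does not identify the condition as an addition to the protocol rule.

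**Working it through.** **1. The plan's own power figure.** Protocol 8.4 gives 48 completers per cell, an effect of 0.7, two-sided 0.05 and 92% power. No SD is stated. Treating 0.7 as a standardised effect (SD = 1.0, an assumption), the noncentrality is 0.7 / √(2/48) = 3.43. The noncentral t with 94 df then gives 92.4%, and the normal approximation gives 92.9%. The plan's figure is reproduced. With the SD at 0.7 or 1.5 instead, the normal approximation gives 99.8% or 62.8%. The within-arm threshold does not enter this calculation.

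**2. The statements side by side.**

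| Place | Bound | Threshold | Direction of change |
|---|---|---|---|
| Protocol synopsis | upper | below -5 | not stated |
| Protocol 8.2.1 | upper | below -0.5 | baseline minus post |
| SAP 6.1 | (hypothesis) | above 0.5 | baseline minus post |
| SAP 6.2 | lower | above 0.5 | improvement positive |

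Ratio of magnitudes: 5 / 0.5 = 10.

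**3. Sign and bound.** With change = baseline minus post, a fall from 6 to 5 scores +1. An upper bound below -0.5 would then demonstrate worsening, which is why the SAP corrects 8.2.1. The synopsis has the same form and, under that definition, the same fault. Reading the synopsis as post minus baseline would rescue the sign but not the size.

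**4. What the scale allows.** Scores run from 1 to 9. Inclusion criterion (e) requires 4-9.

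- Largest improvement = baseline - 1: 3 points from 4, 5 from 6, 8 from 9. A mean improvement above 5 therefore needs a mean baseline above 6. With a mean baseline of 8, the Week 12 mean would have to be below 3.
- Largest worsening = 9 - baseline: 5 points from 4, 3 from 6. If every baseline were at least 4, a mean worsening above 5 could not occur.

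The entry score is the PI's score at Visit 1, not the three-grader baseline, so these are practical limits and not strict ones.

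**5. What each threshold demands, as improvement.** Observed mean needed = margin + t(0.975, 47) × SD / √48, with n = 48 from the protocol and t = 2.012. At SD 1.0 the added term is 2.012 / 6.928 = 0.29. The SDs and true improvements are assumptions.

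| SD of change | Needed, margin 0.5 | Needed, margin 5 | Success at true improvement 1.0, margin 0.5 | Same, margin 5 |
|---|---|---|---|---|
| 0.7 | 0.70 | 5.20 | 99.8% | 0.0% |
| 1.0 | 0.79 | 5.29 | 92.4% | 0.0% |
| 1.5 | 0.94 | 5.44 | 61.9% | 0.0% |

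At margin 5 the probability is still 0.0% with a true improvement of 3.0, at each of these SDs.

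**6. The grader clause.** In SAP 6.2 the 0.5 margin and its confidence bound are attached to the mean improvement score. The clause on individual graders names neither. SAP 6.1 gives 0.5 as the only margin for within-treatment change and does not restrict it to averaged scores. SAP 6.4.2 repeats the primary analysis for each grader. The natural reading is the 6.1 test applied grader by grader, although the text does not say so and a margin of 0 is not excluded.

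**The case against.** The strongest reply is that this is editorial. SAP 6.2 restates the whole decision rule, SAP 6.1 sets the same 0.5 margin, and the protocol's own statistical section also carries 0.5 in magnitude. An analyst following the SAP would never apply 5. The -5 may also be a conversion loss from a figure printed as -.5; the text supplied cannot settle that. All of this stands, and it limits the consequence. It does not make the synopsis right as it reads. The SAP note does not reach it, and a lost decimal would still leave the sign and bound to be reconciled.

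Four stronger readings might be inferred, and the documents do not support them.

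- **That the trial will be judged against 5 and cannot succeed.** The SAP's operative rule is explicit at 0.5.
- **That a mean change of 5 is strictly impossible.** It needs a mean baseline above 6, which entry at 4-9 permits. It is unrealistic, not impossible.
- **That the error damages the sham comparison or its power.** The ANCOVA hypothesis in SAP 6.1 is a difference of zero between arms, and the threshold appears in neither that test nor the power calculation.
- **That the grader clause leaves the success rule open or makes false claims easier.** SAP 6.1 and 6.4.2 supply a natural criterion. Because the clause is an extra condition that must also be met, it can only make the within-arm claim harder to reach.

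**Conclusion.** The point holds for the synopsis. Its threshold is ten times that of section 8.2.1 and, under the definition of change in 8.2.1 and the SAP, it has the wrong sign and the wrong bound. Neither the SAP note nor the version 2.0 amendment corrects it. It should be fixed because it misstates a decision rule on the primary variable in the protocol's own summary.

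The effect is confined to the within-arm claim against baseline. The study objective is the comparison with sham, and that analysis and its 92% power are unaffected. The tenfold ratio and the scale limits rest on the documents alone, subject to the source page confirming that -5 is what is printed. The success probabilities rest on the assumed SDs and true improvements. The grader clause is a matter of clarification, not a contradiction.

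**What to change.** 1. Check the source page of the synopsis for a lost decimal point.
2. Align the synopsis and protocol 8.2.1 with the SAP rule: change is baseline minus post-baseline, and superiority to baseline requires the lower bound of the two-sided 95% confidence interval for the three-grader average to exceed +0.5.
3. Extend the note in SAP 6.2 so that it names the synopsis as well as 8.2.1.
4. In SAP 6.2, state that a grader's result counts as superior to baseline when the SAP 6.1 test is met on that grader's scores (lower 95% bound above 0.5), if that is the intent. Record the two-of-three condition as an addition to the protocol rule.

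All four should be settled before unblinding. The cost is wording in the synopsis, section 8.2.1 and SAP 6.2, with sponsor and IRB/IEC handling of the protocol change under section 10.1. No data collection, sample size or subject procedure changes.

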## LIST OF ABBREVIATIONS

Abbreviation	Definition
AE	Adverse Event
AIDS	Acquired Immunodeficiency Syndrome
ANCOVA	Analysis of Covariance
DPR	Designated Physician Representative
EDC	Electronic Data Capture
EIU	Exposure In Utero
FDA	US Food and Drug Administration
████	████████████████████
HIPAA	Health Insurance Portability and Accountability Act
HIV	Human Immunodeficiency Virus
HRT	Hormone Replacement Therapy
ICD	Informed Consent Document
ICH GCP	International Council for Harmonisation Good Clinical Practice
ID	Identification
IEC	Independent Ethics Committee
IP	Investigational Product(s) (i.e. test products)
IRB	Institutional Review Board
ITT	Intent-to-Treat
LED	Light-Emitting Diode
██	████████████████
LOCF	Last Observation Carried Forward
OTC	Over-the-Counter
PI	Principal Investigator
████	████████████████████
PQC	Product Quality Complaint
PTAE	Pre-Treatment Adverse Event
SAE	Serious Adverse Event
SM	Study Manager
SMF	Site Master File
SPF	Sun Protection Factor
TMF	Trial Master File
████	████████████████████
UV	Ultraviolet
██	████████████████
████	████████████████████

## **1. INTRODUCTION**

Exposure to sunlight and artificial light sources containing ultraviolet (UV) radiation is known to accelerate the skin's aging process, resulting in unwanted wrinkles, irregular skin tone, and loss of elasticity. Ablative techniques, such as dermabrasion, deep chemical peels, and ablative laser resurfacing of various wavelengths, are well documented to alleviate the signs of photodamage. However, such techniques often require significant post-treatment care and have higher risk profiles than other treatments, with potential side effects including erythema, pigmentation issues, infection, and possible scarring. They may be poorly tolerated by patients who dislike the discomfort, wound care, and prolonged downtime involved.

Non-ablative skin rejuvenation procedures are also effective for improving the appearance of photodamaged skin and are becoming increasingly popular because of their minimal downtime and increased safety. These procedures include intense pulsed light systems, non-ablative lasers, and monochromatic light boxes, which can target facial rhytids, irregular pigmentation, telangiectasia, and skin laxity. Unfortunately, such techniques can be expensive and their use is primarily limited to clinical settings.

However, the light-emitting diode (LED) is a novel light source that is well-suited for non-ablative phototherapy that can be utilized at home for a relatively low price. This study will evaluate the efficacy and tolerance of an LED-based light therapy mask as compared to a sham mask in subjects seeking anti-aging benefits.

## **2. OBJECTIVE**

The objective of this study is to evaluate the efficacy and tolerability of an investigational light therapy mask in comparison to a sham mask device over a 12-week usage period and after a 12-week regression period for subjects with mild to moderate mottled hyperpigmentation and moderate to severe facial wrinkles.

## **3. STUDY DESIGN**

This is a single-center, 2-cell, sham-controlled, randomized, evaluator-blinded clinical usage study utilizing three Expert Graders (i.e. the PI plus two additional board-certified dermatologist Expert Graders; see Appendix XI). Up to approximately 125 subjects will be enrolled to finish with at least 96 subjects (targeting 48 subjects per cell). The target population is 35- to 70-year-old females with mild to moderate mottled hyperpigmentation on the face and moderate to severe facial wrinkles. Enrollment will be evenly distributed across all Fitzpatrick skin types (i.e. an approximately equal number of subjects will be enrolled per skin type per cell).

Subjects will be assessed at Screening, Baseline (Week 0), Week 1, Week 4, Week 12, and Week 24, as described in section 7.

At Screening (Visit 1), each subject will be provided with an auxiliary cleanser (twice daily usage – morning and evening) and an auxiliary moisturizer (once daily usage in the morning after cleansing [plus additional evening usage (after completing the mask treatment, as applicable), as desired]) to use full-face for the duration of the study. At Baseline (Visit 2), each subject will be randomly assigned to also use either the

active or sham light therapy mask (with respective activator; once daily usage for 10 minutes in the evening after cleansing) for the 12-week treatment period of the study. The active and sham masks will be identical in appearance; the Expert Graders will be blind to the IP assignment, and subjects will also be blinded to the extent possible (see section 6.6).

A 12-week regression period will begin at Week 12 (Visit 5); during the regression period, subjects will continue using the auxiliary products as described previously, but there will be no mask usage.

